3.7 Protocol and study procedures

All study procedures will be performed during 2 days at least 24 hours apart. Air sampling of the hospital patient's room environmental will be obtained according to the ISPE guidelines for the monitoring of pharmaceutical powders in working environments (14). In particular, five suction

XR5000 pumps (SKC Inc., Eighty Four, PA) containing a filter and running at 5 L/min for 15-20 minutes will be positioned around the patient's bed at different heights and distances (Figure 1) to allow control (i.e. before saline nebulisation) air samples collection. During the air-sampling period, patients will be free to talk and/or cough. After sampling for 15-20 min, the airborne viral load captured within the pump filter will be detected and quantified using a real-time polymerase chain reaction assay. The control air sampling will be repeated for three times at least 2 hours apart to obtain an average viral load. After sampling of control air, each patient will be requested to breathe normally for 3-5 min through a mouthpiece connected to a sampling T adapter, with one end of the T sampling connected to a six-channel optical particle counter (OPC, Climet, Ultimate 100, Redlansa, CA) to measure expired particle count and size. Each channel on the OPC tabulates particle counts within a size-selective range of six bins (0.3-0.5 μ m, 0.5-1 μ m, 1-3 μ m, 3-5 μ m, 5-10 μ m and >10 μ m). The other end of the T sampling will be connected to a Delbag-Luftfilter air filter (COPULAR CKL Macropur-F Acelan, GEA, Berlin), for removal of any airborne particulates from the inhaled ambient air stream (Figure 2). All the above reported procedures will be repeated on the subsequent day before and 5, 30, 60 and 120 min after nebulisation of 0.9% saline delivered by means of a PARI LC Plus Jet nebuliser (PARI, Starnberg, Germany) connected to a compressed air source at 18 psi.

Cleaning and disinfection of the OPC will be carried out at the end of each investigation with vaporized hydrogen peroxide as suggested by Climet Instruments Company.

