The severe acute respiratory syndrome coronavirus 2 (SARS-CoV-2), which causes COronaVirus Disease 2019 (COVID-19), has resulted in a worldwide pandemic and currently represents a major public health (1). The SARS-CoV-2 virus, an acute respiratory infectious agent, is primarily transmitted between people through respiratory droplets and contact routes (2,3). A recognized key to transmission of COVID-19, and droplet infections generally, is the dispersion of bio-aerosols from the patient. Bio-aerosols are defined as aerosols or particulate and matter of animal, plant or microbial origin with a range from 0.1 to >100 µm in diameter (4), that can contain viruses, bacteria, fungi, and are generated by infected persons when they cough, sneeze, talk, sing, or breathe. They can land in the mouth, nose, or eyes of those in proximity, and they have the potential to be inhaled into the lungs.

National and international guidelines recommend droplet/airborne and contact precautions for those caring for COVID-19 patients in ambulatory and acute care settings (5-9). An increased risk of transmission has been associated with aerosol generating procedures, including nebulised treatment. Despite the lack of evidence, there is currently a heightened concern regarding the potential risk of transmission of SARS-CoV-2 in the form of aerosolised respiratory droplets from patients with COVID-19 undergoing nebulised treatment (9,10). Studies regarding risk of spreading the virus in the environment during nebulisation are conflicting. For example, one study reports not to find the virus in hospital air samples near COVID-19 patients (11); in contrast, another study conducted using a manikin in a laboratory detected the virus at a distance of two meters (12). Despite the absence of any robust scientific evidence, some guidelines have advised against the

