use of nebuliser treatment unless absolutely necessary, others have recommended the continued use of nebulised treatment when applicable (see 9 for further refs). Aerosols generated by a nebuliser is derived from a medication solution and is not a bioaerosol - potentially infectious - as that generated during cough or sneeze. However, nebulisers could generate fugitive emissions during the drug administration, which are added to patient expiration potentially infectious (9). Moreover, aerosol delivery devices, including nebulisers, could be theoretically considered as fomites, and, therefore, required strict hygiene rules before, during and after use (9). Interestingly, it has been reported that, in healthy volunteers, nebulisation of isotonic saline reduced the number of exhaled bio-aerosol particles expired by 72% for up to 6 hours due to modifications of the surface tension and viscous forces acting on lung-lining fluid (13). Whether nebulisation of isotonic saline aerosols may reduce exhaled particle also in patients affected by viral infection, including SARS-CoV-2, is unknown.

Hence, this project aims at investigating the effects of isotonic saline nebulisation in patients with SARS-CoV-2 infection. We hypothesise that isotonic saline nebulisation may transiently reduce the number of exhaled bio-aerosol droplets with no significant diffusion of virus in the environmental caused by the nebulisation.

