3.6 Outcome endpoints

Endpoints will be the count of bio-aerosol exhaled particles within a preselected size-selective range (see protocol and study procedures), as well as changes in SARS-CoV-2 degrees in the hospital patient's room environment after 0.9% saline nebulisation.

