3.8 Sample size and data analysis

Due to the explorative nature of the study, a formal assessment of study power will not be performed. However, based on previous studies performed on healthy subjects (13), we estimate that about 10 patients will be sufficient to obtain the data. Parametric variables will be presented as mean \pm SD, with their minimum, maximum and median, while the discrete data will be presented in contingency tables with percentages. Paired t-test will be used to assess differences in the particle size distribution as well as in the SARS-Cov-2 levels before and after nebulisation. The value for the statistical significance will be $P < 0.05$.

4. Safety

All adverse events occurring during thorough the study will be recorded and documented by the Principal Investigator. Any serious adverse event will be reported as soon as possible to the independent Ethics Committee approving the study, according to the current local and national regulations. Expedite reporting will be performed by the Principal Investigator in case of any suspected, unexpected, serious adverse reaction or in case of other safety issues that qualify for expedite reporting, in accordance with the European Directive 2001/20/EC

5. Ethical Considerations

The protocol has been written, and the study will be conducted according to the Declaration of Helsinki and the ICH Harmonized Tripartite Guidelines for Good Clinical Practice. Furthermore, the study will be conducted in accordance with the Ministerial Decree of 17 December 2004.

The final protocol and the final version of the informed consent form will be approved by the local independent ethics committee (IEC) before the study can be commenced. The Principal Investigator is also responsible for informing the IEC of any amendment to the protocol. The Principal Investigator will provide the IEC with reports of Serious Adverse Events from the study site as per local and national requirements. The Principal Investigator will ensure that the patients are given full and adequate oral and written information about the nature, purpose, possible risk and benefit of the study. Patients must also be notified that they are free to discontinue from the study at any time. The patients will be given the opportunity to ask questions and allowed time to consider the information provided. All patients will be requested to provide a signed and dated informed consent before conducting any study-related procedures.

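### Section 3.7 has no step to mark or separate coughs during the 3-5 min particle count, so in COVID-19 inpatients a cough enters the Aim 1 endpoint and cannot be taken out later

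*Protocol*

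**What the plan says.** Protocol section 3.7 describes the Aim 1 measurement: "each patient will be requested to breathe normally for 3-5 min through a mouthpiece connected to a sampling T adapter". The counter sorts particles by size only: "Each channel on the OPC tabulates particle counts within a size-selective range of six bins". The reading is made before nebulisation and four times after it: "repeated on the subsequent day before and 5, 30, 60 and 120 min after nebulisation of 0.9% saline".

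Section 3.6 defines the endpoint in terms of the same output: "Endpoints will be the count of bio-aerosol exhaled particles within a preselected size-selective range". It does not limit the count to quiet breaths, and it gives no unit such as a rate per minute.

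The background, ahead of section 2.0, lists the sources of bio-aerosols, which "are generated by infected persons when they cough, sneeze, talk, sing, or breathe". Its only effect size is a result in healthy volunteers, where "nebulisation of isotonic saline reduced the number of exhaled bio-aerosol particles expired by 72% for up to 6 hours". Section 3.8 relies on the same work in healthy subjects: "we estimate that about 10 patients will be sufficient to obtain the data".

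Section 3.7 mentions coughing once: "During the air-sampling period, patients will be free to talk and/or cough". That sentence belongs to the 15-20 min room-air sampling with the suction pumps (Aim 2), not to the mouthpiece count. It shows only that the protocol foresees coughing in these patients. No section says what happens if a patient coughs on the mouthpiece.

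**The concern.** The manoeuvre requested is normal breathing, and the 72% figure describes exhaled particles in healthy people. The trial population is patients admitted with COVID-19 (section 3.3), and cough is not a named exclusion in section 3.4. A cough is a burst from a source that the protocol itself lists separately from breathing, and a counter that sorts by size alone cannot tell the two apart.

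Two things are at stake:

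- **Noise and dilution.** If coughs are equally frequent before and after, they add variance and pull the after/before ratio towards 1.
- **Bias.** Inhaling an aerosol may change how often a patient coughs. The count would then move with cough frequency, and a change in coughing would be reported as a change in exhaled particles.

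This has to be settled in the protocol because the information exists only at the bedside. If the reading is kept as one total and coughs are not noted when they happen, an analysis plan has nothing to work with.

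**Working it through.** The plan has no figure of its own to reproduce here: section 3.8 waives a power calculation and gives no SD.

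**Inputs from the protocol.** Window T = 3 to 5 min (3.7); expected fall 72%, so an after/before ratio of 0.28 (background); about 10 patients and a paired t-test at P < 0.05 (3.8).

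**Inputs assumed.** k = the particles in one cough, expressed as minutes of that patient's own baseline breathing; number of coughs per window. The documents give neither.

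**1. One cough in one reading after nebulisation, none before.** Baseline count is T and the after count is 0.28T + k, both in minutes of baseline breathing. The fall disappears when 0.28T + k = T, so k = 0.72T:

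- T = 3: k = 2.16 min
- T = 4: k = 2.88 min
- T = 5: k = 3.60 min

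At an assumed 12 to 20 breaths/min this is 0.72 × 36 = 26 to 0.72 × 100 = 72 breaths from a single cough.

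**2. The same cough placed elsewhere (T = 4, k = 2.88).**

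- Before only: 1.12 / (4 + 2.88) = 0.16, an apparent fall of 84%, which exaggerates the effect.
- One in each reading: (1.12 + 2.88) / (4 + 2.88) = 0.58, an apparent fall of 42%. It shrinks but does not vanish.
- After only, with saline also cutting the cough's particles by 72%: 0.28 × (4 + 2.88) / 4 = 0.48, an apparent fall of 52%. Full cancellation would then need k = (0.72 / 0.28) × T = 2.57T, or 7.7 to 12.9 min.

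**3. No true saline effect, but cough frequency changes.** T = 4, one cough per window on average before, k = 3. Expected count before: 4 + 3 × 1 = 7.

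- Frequency halved: (4 + 3 × 0.5) / 7 = 5.5 / 7 = 0.79
- Frequency doubled: (4 + 3 × 2) / 7 = 10 / 7 = 1.43

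On the log scale with Poisson coughs, the geometric-mean ratios are about 0.80 and 1.42. With k = 1 the expected-count ratios are 4.5 / 5 = 0.90 and 6 / 5 = 1.20; with k = 10 they are 9 / 14 = 0.64 and 24 / 14 = 1.71.

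**4. Study level, illustration only.** Assumptions: 10 patients, paired t-test on log counts, log SD 0.4 per reading, T = 4, a true 72% fall, Poisson coughs, equally frequent before and after.

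| Coughs per window | k (min) | Other | Power |
|---|---|---|---|
| none | – | | above 99% |
| 1 | 1 | | 98% |
| 1 | 3 | | 55% (ratio about 0.47) |
| 1 | 10 | | 15% |
| 0.2 | 3 | | 97% |
| 1 | 3 | four after-readings averaged | 87% |
| 1 | 3 | saline also cuts cough output 72% | 99.9% |
| 1 | 10 | saline also cuts cough output 72% | 86% |

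The result depends almost wholly on inputs that the documents do not supply.

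**The case against.** The strongest reply is that the protocol never says coughs are kept in the count. It asks for normal breathing, which defines the manoeuvre, and repeating a spoiled manoeuvre is ordinary operating practice that may be written elsewhere. This stands in part: that coughs enter the total is an inference from silence and from a counter that sorts only by size. But the protocol refers to no such procedure for coughs, and an analysis plan cannot recover an event that nobody recorded.

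A reader might infer that one cough can cancel the whole expected saline effect. The documents do not support that. The break-even concerns one patient's reading at one time point. It needs a cough after nebulisation and none before, cough output unaffected by saline, and a cough yield that the documents do not give. The mechanism described in the background, a change in the lung-lining fluid, could lower cough particles too. A reader might also take the sentence that allows talking and coughing as a rule for the mouthpiece count; it governs the room-air pumps.

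It is also fair to say that power is a weak yardstick in a study that waives a power assessment as explorative, and that section 3.6 does not restrict the endpoint to tidal breaths. Simply dropping cough intervals would narrow that endpoint and would condition on an event that nebulisation may change. This objection stands and shapes the fix: the rate over all intervals must be reported as well.

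**Conclusion.** The concern holds as a gap in the measurement procedure. Section 3.7 gives no step to mark or separate coughs in a totalling count taken from patients in whom coughing is foreseen, and the loss is permanent once the reading is over.

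Its size is not known. For a single after-reading, a cough worth 0.72 × T (2.2 to 3.6 min of baseline breathing) would hide a 72% fall, and a cough in the before-reading would exaggerate it. With no true effect, one cough per 4-min window before and a cough worth 3 min of breathing, halving or doubling cough frequency gives an apparent ratio of about 0.80 or 1.42. Across plausible assumptions the study-level damage runs from negligible to severe. The documents do not support saying that the study's result would be cancelled, nor that the plan sets out to treat coughs as breathing. The change should be made because it is cheap and cannot be made afterwards.

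**What to change.** In section 3.7:

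- Read the counter in short fixed intervals (for example 30 s).
- Have the operator running the counter mark each interval that contains a cough.
- Continue until 3 min of unmarked breathing are obtained, where feasible.

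In section 3.6:

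- Define the particle endpoint as the count rate per minute, by size bin, over unmarked intervals.
- Report alongside it the rate over all intervals, marked and unmarked.
- Report the number of coughs before and after nebulisation.

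The two rates together show whether a change lies in breathing, in coughing or in both. A rate also settles the unfixed window: with raw totals, 3 min before and 5 min after would turn a 72% fall into 1 − 0.28 × 5/3 = 53%.

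The cost is protocol wording and a mark sheet. Some readings will take a few minutes longer, and a patient who coughs often will contribute fewer unmarked intervals.

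### Particle counts and filter loads are compared before and after nebulisation over sampling times that may differ (3–5 min and 15–20 min), with no equal-duration rule and no division by time or volume

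*Protocol*

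**What the plan says.** - **Particle endpoint.** Protocol section 3.6: "Endpoints will be the count of bio-aerosol exhaled particles within a preselected size-selective range". In section 3.7 the patient is to "breathe normally for 3-5 min through a mouthpiece connected to a sampling T adapter", and "Each channel on the OPC tabulates particle counts within a size-selective range of six bins". The counter's sampling flow is not given.
- **Viral endpoint.** Section 3.6 names "changes in SARS-CoV-2 degrees in the hospital patient's room environment after 0.9% saline nebulisation", without a unit. In section 3.7 each pump is described as "containing a filter and running at 5 L/min for 15-20 minutes", after which "the airborne viral load captured within the pump filter will be detected and quantified using a real-time polymerase chain reaction assay".
- **Control air.** "The control air sampling will be repeated for three times at least 2 hours apart to obtain an average viral load". The average is of loads; no weighting by volume is stated.
- **Repetition and analysis.** Section 3.7 repeats the procedures on the second day before nebulisation and at 5, 30, 60 and 120 min after it. Section 3.8 compares before with after by paired t-test at P < 0.05 in about 10 patients.

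Nowhere does the protocol set a single duration, require equal durations within a patient, require actual times to be recorded, or convert either measure to a rate or a concentration.

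**The concern.** A count and a filter load both accumulate with sampling time. When the time may differ between the two members of a pair, the paired difference reflects emission multiplied by duration rather than emission alone. Both aims are exposed: a shorter reading after nebulisation would look like the hypothesised fall in exhaled particles, and a shorter pump run would look like less virus in the room air. The second matters because that aim is about the risk of spreading virus.

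The protocol itself sets the endpoint, the variable windows and the test. A statistical analysis plan could add a denominator, but it could not recover a rate if the actual times were never written down.

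**Working it through.** **Inputs from the protocol.** Breath sampling 3–5 min; air sampling 5 L/min for 15–20 min (section 3.7); about 10 patients, paired t-test, P < 0.05 (section 3.8; two-sided assumed); a 72% reduction cited from healthy volunteers (background). The protocol gives no SD, target difference or power and disclaims a power assessment, so it has no figure of its own to reproduce here.

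**Assumptions not in the protocol.** Constant emission and air concentration within a reading. For the raw-scale simulation: between-patient log SD 0.8 and within-patient CV of 20%, 30% or 50%.

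**1. Duration factor.** Expected count = rate × minutes. Filter load = concentration × 5 L/min × minutes. So the observed after/before ratio = true ratio × (minutes after ÷ minutes before).

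**2. Worst case with no true effect.**
- Particles, 5 then 3 min: 3/5 = 0.60, a 40% fall. 3 then 5 min: 5/3 = 1.67, a 67% rise.
- Air volume: 5 × 15 = 75 L and 5 × 20 = 100 L. 20 then 15 min: 75/100 = 0.75, a 25% fall. 15 then 20 min: 100/75 = 1.33, a 33% rise.

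**3. Worst case with a true effect.**
- A true 40% fall with 3 then 5 min: 0.60 × 5/3 = 1.00, cancelled.
- A true 33% rise in virus with 20 then 15 min: 1.33 × 0.75 = 1.00, cancelled.
- A true 72% fall: 0.28 × 5/3 = 0.467, read as 53%; 0.28 × 3/5 = 0.168, read as 83%.

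**4. Random variation only.** If each duration is uniform on 3–5 min, independent of period, the SD of log(duration) is 0.1465, so the log ratio gains SD √2 × 0.1465 = 0.207. For an assumed 30% reduction (log 0.70 = −0.357) and within-patient log SD 0.2, the SD of the paired log difference is √(2 × 0.2²) = 0.283 with equal times and √(0.283² + 0.207²) = 0.351 with variable times. At n = 10, power is 94% and 82%.

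**5. Simulated paired t-tests** (n = 10, 40,000 runs, raw scale), percentage with P < 0.05:

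| Scenario | CV 20% | CV 30% | CV 50% |
|---|---|---|---|
| No effect, equal times | 3 | 3 | 3 |
| No effect, random 3–5 min | 3 | 3 | 3 |
| No effect, 5 then 3 min in every patient | 89 | 68 | 34 |
| No effect, 4.5 then 3.5 min in every patient | 46 | 24 | 10 |
| No effect, air 15 then 20 min in every patient | 57 | 30 | 13 |
| True 40% fall, equal times | 89 | 69 | 34 |
| True 40% fall, random 3–5 min | 80 | 60 | 31 |
| True 72% fall, equal times | 96 | 94 | 86 |
| True 72% fall, 3 then 5 min in every patient | 94 | 88 | 60 |

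On the log scale the null rejection rate is about 5% with equal times and also about 5% with random times.

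**6. Does the schedule force shorter readings?** Taking the air run and then the breath reading from the 5-min point, the longest permitted sequence is 20 + 5 = 25 min. That ends exactly at 30 min, when the next set is due. The shortest is 15 + 3 = 18 min, which leaves 7 min. The later gaps are 30 and 60 min. So one interval has no slack at the upper limits, but even there the longest sequence fits.

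**The case against.** The protocol says count, levels and degrees; it never says unadjusted total. Only the protocol is at hand, and a statistical analysis plan may define the unit. The pump flow is stated, so a concentration could be derived if run times were kept. This is fair as far as it goes, but the protocol does not require run times to be kept, and without them no later document can supply the denominator.

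If section 3.8's comparison of the particle size distribution is analysed as shares per bin, duration cancels. That stands for shares. It does not help the count that section 3.6 names as the endpoint.

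A reader might infer that readings after nebulisation will be systematically shorter and will therefore mimic a benefit. The documents do not support this. Nothing in them says so, the longest sequence just fits the tightest gap, and the later gaps are wider. The 40% and 67% figures also need opposite extremes before and after, in every patient, to become a bias of that size in the group mean.

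For virus, a 1.33-fold volume difference is log₂(1.33) ≈ 0.4 PCR cycle if each cycle doubles the product, and averaging three control runs dampens random variation in duration on that side. Both points reduce the practical size of the artefact; neither removes a systematic difference.

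Finally, this is an explorative study of about 10 patients with no power claim. That limits the weight of the power figures but not the need for an endpoint that measures emission.

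**Conclusion.** The point holds: as written, the before/after contrast mixes emission with sampling time, for both endpoints.

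- **Systematic difference in duration** (possible, not shown to be likely): a worst-case artefact of −40% or +67% for particles and −25% or +33% for virus. These bounds follow from the protocol's own windows and from constant emission within a reading.
- **Random difference only:** false positives are not inflated. The cost is precision: 94% to 82% power in the example above, or 89% to 80%, 69% to 60% and 34% to 31% for a 40% fall at CVs of 20%, 30% and 50%. The effect sizes and variabilities are assumptions.
- **An effect as large as 72%:** a reader might infer that it could be concealed. It could not; it would read as 53% to 83%, still a clear fall. At the highest assumed CV, however, the chance of significance drops from 86% to 60% in the extreme case. Moderate effects, near a 40% fall in particles or a 33% rise in virus, are the ones that opposite extremes could cancel.

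**What to change.** - **Section 3.7:** set one duration for each measurement, used at every time point on both days and chosen so that the whole sequence fits between the 5- and 30-min points; 20 + 5 min would leave no slack. Failing that, require actual start and stop times to be recorded for every reading and pump run.
- **Sections 3.6 and 3.8:** define the particle endpoint as particles per minute in each size bin (per litre only if the counter's sampling flow is stated). Define the viral endpoint as RNA copies per m³ of air = 1000 × copies ÷ (5 L/min × actual minutes), where 1000 converts litres to m³. Average the control runs on that scale.

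Under constant emission, the duration factor is then 1 at any permitted time. A fixed duration is the better option: if emission changes after nebulisation, windows of different length average over different periods, and a 75 L run has a detection limit per m³ 1.33 times that of a 100 L run.

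The cost is two recorded times and one division, and slightly less flexibility at the bedside if the duration is fixed. The rule is needed before sampling starts, because unrecorded times cannot be recovered.
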